Management of Chronic Pain and PTSD in Gulf War Veterans With tDCS+Prolonged Exposure

NCT04236284

Version Date: 03/26/2020

1. ABSTRACT (provide a one-paragraph summary of the current seed project)

Veterans with co-morbid chronic pain and PTSD utilize healthcare services at a higher rate than those with pain or PTSD alone. Unfortunately, there are no integrated treatments for Pain and PTSD. Moreover, non-pharmacological treatments for pain such as Cognitive Behavioral Therapy are useful in only about 50% of cases. Transcranial direct current stimulation (tDCS) may be an effective treatment for pain, and has been recently used to ameliorate PTSD symptoms. Prolonged Exposure Therapy (PE) is highly effective in treating PTSD symptoms. *Therefore, we propose to (a) integrate & (b) gather feasibility data for home-based tDCS + PE for Pain and PTSD with 15 Veterans.*

2. PRIMARY HYPOTHESES AND SPECIFIC AIMS (provide an NIH-style set of primary hypotheses about the project outcomes, and the specific aims that will be accomplished)

Chronic pain is one of the most prevalent health conditions among Americans, affecting about a third of the general population¹. In Veterans, chronic pain is even more common, with a prevalence of about 50%^{2,3,4,5}. For instance, the pain-related fibromyalgia diagnosis is part of Gulf War Syndrome and is highly comorbid with other common military service-related health problems such as Posttraumatic Stress Disorder (PTSD)⁶. Moreover, lack of effective, integrated, and available alternative treatments for chronic pain contributes to the opioid epidemic⁷. Combat veterans are more likely to develop PTSD than civilians, with 20-30% of Vietnam-era Veterans, 15-25% of Operation Desert Storm Veterans, and 11-25% of Operation Enduring Freedom, Operation Iraqi Freedom, and Operation New Dawn (OEF/OIF/OND) Veterans experiencing significant PTSD symptoms^{8,9}. The number of veterans with chronic pain and PTSD is expected to grow given the return of personnel from recent OEF/OIF/OND conflicts^{9,10}. Veterans with co-morbid chronic pain and PTSD utilize healthcare services at a higher rate than those with pain or PTSD alone, leading to an increased burden on healthcare systems throughout the United States. Furthermore, opioid medications have been used more frequently to treat chronic pain among OEF and OIF Veterans with PTSD, and these Veterans are more likely to incur harmful consequences during the course of their care due to these medications¹².

The Overall Aim of the present proposal is to integrate, refine and investigate the feasibility (e.g., pilot testing, recruitment, attrition, assessment) of tDCS for treating chronic pain with a best practices evidence-based treatment for PTSD (i.e., Prolonged Exposure: PE) in 15 veterans, a group for which both pain and PTSD are particularly problematic.

SA1: Integrate the home-based tDCS+PE Treatment. The investigative team is comprised of Pain, PTSD, and salivary biomarker experts who will integrate tDCS into the 12 session PE treatment protocol.

H1: The 12 session PE protocol will yield itself well to tDCS component integration based on participant feedback.

SA2: Test the feasibility of both the integrated intervention and key study design features, including translational research features such as biomarker assessment in a non-randomized trial with 15 Veterans assessed at baseline and post-treatment. Feasibility of the home-based tDCS+PE intervention will be measured in terms of recruitment metrics, assessment burden, successful biomarker collection, specification of biomarker relationship to hypothesized mechanisms of change, treatment attrition, rates of missing data at each measurement time point, participant satisfaction, and ratings of treatment face validity. Post treatment key informant interviews will be conducted where suggestions for treatment enhancement and satisfaction will be systematically collected and analyzed.

H2 is given in terms of *Specific Pre-Defined Milestones for Success, including: 75% of Veterans experiencing chronic pain and PTSD who enroll will complete at least 8 sessions of the integrated treatment, and both completers and dropouts will offer actionable suggestions in exit interviews for improving the delivery of the intervention. SA2) Feasibility metrics will be acceptable for recruitment rate (two per month), treatment completion of 8 sessions (75%), assessment completion (90%), and good to excellent satisfaction (95%).*

3. BACKGROUND AND RATIONALE (provide evidence for the importance of the scientific/clinical problem, and how this project will address the problem, including new knowledge to be gained)

[figure not shown]
Chronic Pain: Chronic pain is common in Veterans, with a prevalence of about 50%^{2,3,4,5}. Moreover, pain is highly comorbid with other common military service-related health problems such as Posttraumatic Stress Disorder (PTSD)⁶. Pain is an exceedingly costly condition, with estimates from the Institute of Medicine at \$560 to \$635 annually for healthcare costs, disability days, and lost wages in the United States¹⁰. Moreover, lack of effective, integrated, and available alternative treatments for chronic pain is a contributor to the opioid epidemic⁷.

Post-Traumatic Stress Disorder: PTSD is characterized by intrusion symptoms, persistent avoidance behaviors, negative alterations in cognition and/or mood, and alterations in arousal and reactivity¹¹. Combat veterans are more likely to develop PTSD than civilians, with 20-30% of Vietnam-era Veterans, 15-25% of Operation Desert Shield and Desert Storm Veterans, and 11-25% of Operation Enduring Freedom, Operation Iraqi Freedom, and Operation New Dawn (OEF/OIF/OND) Veterans experiencing significant PTSD symptoms^{8,9}.

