4. INNOVATION

The means by which the current proposal addresses a widely prevalent problem (i.e., Pain comorbid with PTSD), and a national crisis (i.e., opioid addiction following pain treatment), is highly innovative, both in terms its treatment integration, and in terms of its use of select biomarkers to specify mechanisms of improvement.

5. METHODS (describe the primary plan for data collection, measurement tools, and timelines)

Design Overview and Project Timeline: The study team will first integrate home-based tDCS into two of the early weeks of the 12 week sessions of PE protocol. The reasoning to conduct tDCS in this way related to PE are three folded: first, controlling signaling of pain to engage into trauma treatment may reduce dropout from PE; second, research shows some cognition improvement with tDCS which may help patients to understand and more adequately participate in aspects PE treatment particularly as the complete understanding of the rationale of PE at the beginning of the treatment is very important to set the stage for treatment expectation and prevent dropout, and finally the hypothesized model of interaction of chronic pain and PTSD symptomatology, tDCS may help to reduce avoidance behavior modulated by pain and PTSD symptoms. This will be followed by a repeated measures single group design wherein each of the 15 Veteran participants serves as their own control, with major assessments of feasibility, clinical and biomarker indices at pre, mid and post-treatment (week 13), complemented by weekly assessments of key pain and PTSD symptoms. The study will also include with open ended key informant interviews following treatment with the 15 participants to derive suggestions for improving the integrated treatment

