6. Rate of Missing Data: defined as % of missing data (# missing items aggregated across all self-report measures divided by total number of possible items) at each measurement time point.
7. Treatment Satisfaction: as measured by the Charleston Psychiatric Outpatient Satisfaction Scale: CPOSS⁶⁰.
8. Treatment Credibility: defined as an overall scale rating from 0 to 10 with 0 being '*not credible, I did not think this treatment would help either my PTSD or Pain symptoms*' to 10 being "*completely credible, I was very sure this treatment would help both my PTSD and Pain symptoms*".
9. Treatment Acceptability: defined as an overall scale rating from 0 to 10 with 0 being '*not acceptable, this treatment should not be offered to veterans, those in pain, or those with PTSD*' to '*completely acceptable*' "*this treatment is perfectly suited to veterans and others with Pain and PTSD symptoms*."
10. General Pain Information (Major Assessments): general information about chronic pain will be gathered to include location of pain site(s), duration of chronic pain at each site, current and prior treatment approaches for chronic pain, medical visits related to pain management, and past pain medications.
11. PROMIS Pain 3a Intensity Scale⁵⁵ (Weekly during Treatment + Major Assessments)
12. PROMIS PAIN 8a Interference Scale⁵⁵ (Weekly during Treatment + Major Assessments)
13. The Clinician-Administered PTSD Scale 5 (CAPS-5)⁶¹ (Major Assessments)
14. PTSD Checklist-5 (PCL-5)⁶¹ (Major Assessments)
15. PHQ-9⁶² (Weekly during Treatment + Major Assessments)
16. World Health Organization Quality of Life – Short Form (WHOQOL-BREF)⁶³ (Major Assessments)

To permit comparison with prior pain research, but to limit participant burden, the following additional pain related scales will also be used only at major assessment points:

17. The West Haven-Yale Multidimensional Pain Inventory: (Major Assessments) (WHYMPI/MPI)⁶⁴
18. The Tampa Scale of Kinesiophobia-Revised (TSK-R)⁶⁵ (Major Assessments)
19. Pain Catastrophizing Scale (PCS)⁶⁶ (Major Assessments)
20. Homework Diary (Weekly During Treatment): Daily records of tDCS and PE homework completion will be maintained so as to permit 'dose as delivered' effects of treatment.
21. Biomarker Assessments (Baseline, Mid-Point, Post-Treatment and Follow-ups): Salivary levels of the biomarker panel (cortisol, substance P, DHEA, IL-1, and IL-6) using enzyme-linked immunosorbent assays (ELISA).

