5.11. Post treatment Key informant interview procedures and Integration of Feedback

A standardized series of queries will be used to prompt participants to comment on various aspects of the intervention integration and how it might be approved. Additional information will be provided in the larger proposal derived from this pilot.

5.12. Treatment Providers / Interviewers / Consent Procedures: Project therapist will have a master's degree or higher in clinical psychology, counseling, or social work and be certified to deliver PE. All treatment sessions will be audio-taped and 15% of these will be randomly selected and rated for adherence. The PI or Research Assistant will conduct the consent procedures and initial eligibility (i.e., baseline) diagnostic assessments for the study. The Research Assistant will conduct all major assessments. All assessments will be audio-taped and study personnel will listen to a randomly selected 20% to ensure reliability of CAPS diagnosis over the course of the study. Pilot trials of this assessment battery indicate that major assessments will take between 75 and 90 minutes.

5.13. DATA ANALYSIS PLAN (provide a detailed description of how the data will be analyzed, focusing specifically on how the data analytic approach is suited to answer the study aims)

Analysis Sets & Treatment of Missing Data: Participants who terminate early will be asked to complete follow-up interviews and their data will be included in analyses following intent to treat standards.

Descriptive Analyses Putative prognostic variables that will be investigated through these descriptive analyses include: demographic factors, number/type of comorbid diagnoses, participation in non-study treatment for comorbid psychopathology, medications (by class), and initial (baseline) intensity/severity levels for the primary outcome variables: pain severity, pain interference, and intensity of PTSD (PCL), avoidance behaviors, and whether non-study treatments were received for psychopathology symptoms. To investigate potential limits on generalizability, we will compare demographic characteristics of those who decline to participate with those who participate.

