Primary Feasibility Analyses *Feasibility Hypothesis SA1) 75% of Veterans experiencing Pain and PTSD who enroll in the Pilot will complete the integrated treatment (at least 8 sessions) and both completers and dropouts will offer actionable suggestions in focus groups for improving the delivery of the intervention.* We will report the % of veterans who complete the integrated tDCS+PE protocol. We will report the rate of treatment completion, including a description of number of sessions completed prior to dropping out at the patient level (with 12 sessions completed being 100% treatment complete/not dropout). In addition to overall measures of treatment completion (i.e., session attendance), we will also collect measures of treatment adherence, as measured by percent of returned, completed homework record forms for tCBS and exposure practices in terms of actual daily assignments completed. All these measures will also be reported in terms of Race and Sex. *Feasibility Hypothesis SA1) Feasibility metrics will be acceptable for recruitment rate (2 per month), treatment completion (75%), assessment completion (90%), and good to excellent satisfaction (95%).* A key feature of the proposed feasibility study is demonstration that recruitment of eligible participants is possible for a future large scale RCT. Thus, we will report all aspects of CONSORT data in addition to the number of referrals obtained each week. Finally, we will report the overall % of missing data at the item level, and the rate of assessment completion and partial completion at each time point to examine if assessment timing is optimal. SA1 also includes effective collection and use of stress biomarker samples. Finally, Descriptive data on rates / scores for satisfaction, credibility, and acceptability will be reported.

6. SUMMARY and SPECIFIC AIMS for ENSUING GRANT APPLICATION (Page 6)

SPECIFIC AIMS

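### Is the 90% assessment-completion milestone too loosely defined to be judged?

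*Combined protocol and SAP*

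**What the plan says.** The target stands in Section 2 (H2), among the pre-defined milestones, as part of "treatment completion of 8 sessions (75%), assessment completion (90" per cent). It is restated without further definition in Section 5.13, Primary Feasibility Analyses.

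The same paragraph of Section 5.13 says the team will "report the overall % of missing data at the item level, and the rate of assessment completion and partial completion at each time point". Item 6 of Section 5.10 defines the item-level figure as "missing items aggregated across all self-report measures divided by total number of possible items", again at each measurement time point, and calls it missing data. Section 5.10 has no entry for assessment completion.

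On who is counted, Section 5.13 (Analysis Sets) says of early terminators that "their data will be included in analyses following intent to treat standards". Section 5.12 describes the baseline work as "initial eligibility (i.e., baseline) diagnostic assessments".

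On the visits, SA2 in Section 2 speaks of a "non-randomized trial with 15 Veterans assessed at baseline and post-treatment", whereas the Design Overview in Section 5 plans "clinical and biomarker indices at pre, mid and post-treatment (week 13"). The payments in Section 5.8 and the saliva schedule in Section 5.10 also include the mid-point.

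**The concern.** A pre-defined milestone should have a numerator and a denominator before data arrive. The treatment-completion target has both: Veterans who enrol, and at least 8 sessions. The assessment target has neither in so many words. Section 5.13 promises more than one completeness figure, and they can fall on opposite sides of 90% for the same data. Baseline doubles as the eligibility assessment, so attendance there is nearly certain, and any rate that pools it with later visits is pushed upward. The two-visit wording in SA2 adds another possible denominator.

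If the choice were truly open, a team could report the milestone as met while a fifth of the sample had no post-treatment data. That would matter in a feasibility study whose results are meant to support a larger trial.

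**Working it through.** **Inputs.** N = 15 (Sections 1, 2 and 5); target 90% (Sections 2 and 5.13); three major assessments (Section 5); treatment-completion target 75% (Section 2). The documents give no expected attendance, so the patterns below are assumptions. The 90% is a set target, so there is no derived figure to reproduce.

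**Count required at one time point.** 0.90 × 15 = 13.5, so 14 Veterans: 14/15 = 93.3%, while 13/15 = 86.7% falls short.

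**Case A (assumed).** Attendance is 15 at baseline, 14 at mid-point and 12 at post-treatment, and attenders complete everything. Twelve is a reasonable test value because 0.75 × 15 = 11.25, so 12 is the fewest Veterans who can satisfy the treatment-completion target.

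| Reading | Calculation | Against 90% |
|---|---|---|
| Each time point, all enrolled | 15/15 = 100%; 14/15 = 93.3%; 12/15 = 80.0% | missed at post-treatment |
| Three visits pooled | (15 + 14 + 12)/45 = 41/45 = 91.1% | met |
| Baseline and post pooled | (15 + 12)/30 = 27/30 = 90.0% | met |
| Post, attenders only | 12/12 = 100% | met |

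**Case B (assumed).** All 15 attend post-treatment and 3 leave a third of the items blank.

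| Reading | Calculation | Against 90% |
|---|---|---|
| Fully complete | 12/15 = 80.0% | missed |
| Complete or partial | 15/15 = 100% | met |
| Item level | 1 − 3 × (1/3)/15 = 14/15 = 93.3% | met |

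**Which readings the text supports.**

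- *Pooling visits.* Section 5.13 reports assessment completion by time point. The word overall in that sentence qualifies the item-level missing-data figure, and may mean across measures, since item 6 of Section 5.10 computes that figure at each time point. No pooled completion rate is planned.
- *Item level.* The plan calls this missing data and restricts it to self-report measures. It is a different quantity from assessment completion.
- *Complete plus partial.* Section 5.13 names the two separately, so a partial assessment is not a completed one.
- *Attenders only.* H2 counts treatment completion from enrolment, and Section 5.13 retains early terminators under intent to treat. Both point to 15 as the denominator.
- *Two visits.* SA2 is a summary sentence. The operational text (Sections 5, 5.8 and 5.10) has three major assessments, so the missing mid-point is a clerical slip.

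This leaves full completion, at each time point, among all 15. Both cases then give a definite answer at post-treatment: missed.

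**Effect of baseline.** With rates shown by time point, the baseline value cannot raise the post-treatment value. Eligibility also makes attendance nearly certain, not completion of the whole battery, which is wider than the diagnostic measures.

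**The case for a change.** The strongest case for a change is that the link between the target and the reported rate is one of wording only. The reported rate is a set of values, one per time point, and the plan does not say whether each must reach 90%. Nor does it say what makes an assessment partial: a missing CAPS-5 interview, one blank item, or a primary outcome that cannot be scored. A single sentence would settle this at no cost, and the milestones are this study's success criteria.

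Those gaps are real. The available text has no rule for complete versus partial and no rule for combining time points into one verdict. Two considerations limit their weight. First, the silence is weak evidence: part of the text between the Design Overview and Section 5.2 was not available, and Section 5.10 states that the measure descriptions were taken out. Second, an analyst has an obvious default, namely the scheduled battery done in full or not. Section 5.13 also names the "primary outcome variables: pain severity, pain interference, and intensity of PTSD (PCL"), which offers a workable fallback. Whichever is used, partial completions and item-level missingness are reported alongside, so a generous rule for completeness would be visible.

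The possibility of choosing a favourable rate afterwards is also limited by the reporting commitment. A team claiming success on a pooled 91.1% would have to print the 80.0% at post-treatment in the same results.

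**Conclusion.** The concern identifies missing detail, but no change to the plan follows. Followed as written, the plan reports completion and partial completion at every time point, and the ordinary reading gives a clear verdict against 90% at each one. The largest pooling effect shown in Case A is 91.1% against 80.0%, or 11.1 percentage points. It needs both the assumed attendance and a way of combining visits that the plan does not propose for this rate.

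The consequence is small. This is a single-arm descriptive study of 15 Veterans. No test, error rate or sample size depends on the target, and no available section attaches an action to missing it. A sharper definition would not make the label much more informative either. If true completion at one visit were 90%, the chance of reaching 14 of 15 is 15 × 0.9^14 × 0.1 + 0.9^15 = 0.343 + 0.206 = 0.549. Readers planning a later trial will rely on the rates by time point, and those are already promised.

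The conclusion rests on three assumptions: that assessment completion means the same thing in both places in Section 5.13, that intent to treat fixes the denominator at all enrolled, and that the unavailable text contains no conflicting rule. If the 90% later became a formal go/no-go criterion for a larger trial, the definition would need to be written out there.

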3.1. Chronic Pain and PTSD: *Figure 1*

Potential for Mutual Symptom

Exacerbation Avoidance of stimuli associated with a traumatic event, as well as hypervigilance (with concomitant increased pain perception) are diagnostic features of PTSD. Patients with chronic pain often exhibit avoidance behaviors secondary to perceived pain related to physical activity, leading to inactivity and weakened overall health status. Indeed, the presence of shared avoidance behaviors may predict poor outcomes for individuals experiencing co-morbid pain and PTSD^{12,13}. Research focused on treatment approaches that address this shared avoidance may be fruitful, given the impact that co-morbid pain and PTSD have on veterans.

Hyperarousal and hypervigilance to bodily sensations are also found independently in chronic pain and in PTSD, although they likely have an additional synergistic effect on maintaining the negative impacts of both conditions when they are comorbid¹². Additionally, other PTSD symptoms such as numbness and detachment from others are also frequently associated with chronic pain¹⁴. Figure 1 presents a thematic diagram illustrating the interaction between core characteristics of PTSD and comorbid pain targeted in the present proposal.

3.2. Transcranial direct current stimulation (tDCS). Noninvasive brain stimulation, such as transcranial direct current stimulation (tDCS), has received significant attention for the treatment of pain in chronic conditions owing to its neuromodulatory effects in the central nervous system¹⁵. tDCS involves the application of low-amplitude direct electric current to the head in a noninvasive and painless manner, which modulates the resting membrane potentials of neurons, altering the excitability of the targeted cortical area. tDCS is categorized as a “non-significant risk” device by the U.S. Food and Drug Administration^{16,17}. Hundreds of clinical trials have demonstrated tDCS to be safe and well tolerated within the established current intensities and durations¹⁸. For pain treatment, stimulation is typically delivered multiple times with the anode electrode placed over the primary motor cortex and with the cathode electrode placed over the supraorbital region. In particular, a panel of experts of the International Federation of Clinical Neurophysiology published evidence-based guidelines in which they recommended 20-minute tDCS using 2 mA electrical current intensity for possible efficacy among populations with chronic pain¹⁹. Our group and others have shown that this stimulation produces analgesic effects by activating afferents or efferents that connect structures involved in pain processing or by facilitating descending pain modulation and improves pain system function through direct effects on the motor, somatosensory, and frontal cortices implicated in pain sensitivity^{20,21}.

3.3. tDCS may potentiate treatment outcomes achieved from PE. Since tDCS is a noninvasive and safe approach to facilitate neuroplasticity²², it may enhance the brain’s ability to adaptively reorganize in response to other clinical interventions²³, including PE. Because the therapeutic effects of PE are at least partially due to adaptive changes in pain-related brain function, pairing tDCS with PE may augment the adaptive brain changes that occur with PE and further reduce pain and PTSD symptoms.

3.4. Saliva as a non-invasive Biomarker source for innovative Pain & PTSD related measures: Saliva contains numerous biomarkers including proteins, peptides, mRNA, DNA, and miRNA of both human and oral microbial origin^{24,25,26,27}. Molecules such as nerve growth factor (NGF), substance P, dehydroepiandrosterone (DHEA), opioidin²⁸ and calcitonin-gene related peptide (CGRP) are secreted in saliva in response to chronic stress and pain^{29,30}. For instance, molecules such as cortisol, DHEA, Substance P, norepinephrine, salivary alpha amylase and estrogen have long been proposed to be useful in diagnosis of PTSD^{31,32,33,34}. The following

are biomarkers that have been proposed to be indicative of development of PTSD symptoms, however not all of them were tested in the saliva (reviewed in Andrews, & Neises³⁵): 1) Neuropeptide Y, released from sympathetic

neurons during chronic and sustained stress³⁶ 2) CD14, associated with TBI, stroke and microglial activity^{37,38} 3) S100A8, marker of microglia and macrophages and elevated in TBI³⁹ 4) S100A10, shown to be reduced in level in PTSD when compared with controls^{40,41} 5) TNF α , a potent inflammatory response initiator elevated in PTSD⁴² (6) IL-1, associated with local and systemic inflammation, elevated in PTSD^{43,44} 7) IL-6, a pleiotropic cytokine elevated in PTSD^{45,46} and 8) GS α , a key intracellular signaling molecule associated with depression and suicide⁴⁷. Recently salivary alpha amylase has been proposed to be a marker for pain in epilepsy⁴⁸ and cancer⁴⁹; salivary cortisol and sTNF α RII have been to some degree associated with pain intensity and pain unpleasantness in healthy individuals⁵⁰; salivary chromogranin A level increases after massage therapy suggesting it could be a marker for reduced pain perception⁵¹. Evidence shows the relevance of tDCS and salivary biomarkers. These studies show that tDCS stimulates salivary proteomic changes, especially related to inflammation and stress. For instance, IL-10, IL-6, TNF-alpha, CRP, Cortisol, and beta-endorphin have been shown to modify after tDCS treatment^{52,53}. As the usefulness of these biomarkers has not yet been fully established in PTSD^{54,54} further validation is critical.

